3.2 Secondary Outcome Measures

Determine the relative impact on residual limb health of the use of a powered prosthesis, a microprocessor-controlled prosthesis, and a passive prosthesis for individuals with transtibial amputation at 4 weeks.

- Transepidermal water loss (TEWL) measurements at 4 weeks
- Skin perfusion measurements and analysis at 4 weeks
- PEQ, CLASS and Comfort Score responses at 4 weeks

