- Body weight recorded.
- Multiple ambulation trials will be performed including level-ground walking tasks, stair ascent/descent tasks, and ramp ascent/descent trials
- 3D motion capture using the motion capture system will be conducted with the use of an electronic device that measures and reports a body's specific force, angular rate, and sometimes the orientation of the body, which are placed on subjects clothing to capture movement
Walking tasks and ascending/descending tasks on stairs and ramps will be completed with the use of force-sensing pads
- Timed get up and go test will be performed: subject will stand from seated position and walk 3 meters and then return and sit down
- Prosthetist will fit the participant with the research foot that was randomized to them
 - 15-30 minutes of usage of the prosthetic foot will be provided for acclimation
- Subject will repeat the level-ground, stair, and ramp trials with the new prosthetic foot (Foot A)
- Prosthetist will remove pressure sensors from the socket after ambulation and recording will be terminated

Upon completion of baseline, the subject will wear the research device (Foot A) for 4 weeks to become accustomed to the new technology through its exclusive use in place of their standard-of-care prosthetic foot.

Study Visit 3: After the four-week acclimation period, the subject will return for Visit 3 at IUH Methodist Hospital. A window of +/- 7 days will be implemented, ensuring the duration to complete Visit 3 remains consistent among all participants. The following activities will take place during Visit 3:

- Participant's weight will be captured
- Research personnel will administer surveys (Socket Comfort Score, CLASS and PEQ-13)
- Non-invasive limb health measurements performed (TEWL and Laser Speckle Imaging (LSI))

- Licensed prosthetist will perform pre-fitting and adjustments on the patient, ensuring the other research foot (Foot B) will be ready to deliver during participant's next visit

Study Visit 4 (Study Visit 3 if opted for 4 Study Visits): Study Visit 4 will occur within a week after Visit 3 with a window of 0-7 days. This visit will take place at Noyes. The following activities will take place:

- Digital shape capture will be performed
- Administer pressure sensors on participant's research socket and recording will be initiated using Foot A
- Body weight recorded.

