7.0 Study Procedures

Socket Comfort Score survey: a subjective measure on an 11-point scale of how comfortable the individual feels in the socket. (“On a 0 to 10 scale, if 0 represents the most uncomfortable socket fit you can imagine, and 10 represents the most comfortable socket fit, how would you score the comfort of the socket fit of your artificial limb at the moment?”).

PEQ-13 survey: a 13-question subset of the Prosthesis Evaluation Questionnaire that focuses on the perceived potential for mobility, ambulation, and transfers while using a prosthetic device.

The PEQ-13 uses a 100-point formatted visual analog scale with a scoring range of 0 to 130 in which a higher score indicates high functioning.

CLASS Survey (Comprehensive Lower Limb Amputee Socket Survey): this survey is a self report measure of socket fit that asks the subject to rate stability, comfort, appearance and suspension for their prosthetic socket.

Pressure Sensors (Tekscan F-Socket System): pressure sensors will be placed inside the socket to quantify the amount of force that the participant puts on their residual limb. The sensors will be trimmed to fit the curvature of the socket interface so that reliable measurements can be made in the distal, medial, and proximal regions on the anterior and posterior surfaces of the socket, as well as the fibular head.

Shape Capture: The experimenter will conduct a 3D scan of the residual limb to capture its shape using an optical tracking CAD/CAM system.

K3 Activity Level: Has the ability or potential for ambulation with variable cadence, typical of the community ambulator who has the ability to transverse most environmental barriers and may have vocational, therapeutic, or exercise activity that demands prosthetic utilization beyond simple locomotion.

TEWL: Transepidermal water loss quantifies the functional integrity of the skin. A breach in the physical integrity of the skin (i.e. ulceration) is preceded by breach of functional integrity of the skin, which is indicated by elevated TEWL measurements. This instrument is a non-invasive probe that is placed on the skin that measures water loss coming from the skin. The PI's prior work has shown that, like socket pressure, TEWL is affected by the type of suspension.

Weight: We will obtain weight at all study visits

Laser Speckle Imaging (LSI): A non-invasive device that measures blood flow, referring to the rate of blood flow through the vessels serving the skin.

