13.0 Statistical Considerations

This longitudinal study will compare the effects of the three prostheses on the various measured quantities for each subject. Motion capture data will be filtered with an 8 Hz Butterworth low-pass filter, and ground reaction forces will be filtered with a 50 Hz critically damped filter. These data will be collected and analyzed primarily to interpret how differences in kinematics and kinetics associated with the prostheses contribute to corresponding differences in socket pressure and limb health measures. All pressure measurements will be normalized with respect to body weight as measured during the session of data collection. Mean peak pressure within and pressure-time integrals across each gait cycle will be calculated for each sensor location. The peak pressure provides an indication of the maximum loading at any location, while the pressure-time integral combines both the magnitude and duration of loading since both are relevant for limb health.

The 3D scans of the residual limb will be compared between Visits 2 and 4 and between Visits 4 and 6 as a means of interpreting whether significant changes in socket pressure are due to corresponding changes in residual limb volume and/or shape. Both TEWL and skin perfusion, i.e., laser speckle imaging, will be measured or quantified into continuous scales from a three-period, baseline, 30 min post-fitting and 4 weeks post-fitting. The values will be normalized using the values collected from the corresponding reference site [62].

Mean peak socket pressure will serve as the primary outcome measure, with particular emphasis on the proximal region of the anterior surface. Pressure-time integrals will serve as the secondary outcome measure, again emphasizing the same region. TEWL values will be used as the primary outcome measure of overall limb health, while skin perfusion will be the secondary outcome measure. For each measure, comparisons among the three prostheses will be made via a repeated measures ANOVA with Bonferroni correction. For both aims, the survey responses will provide a means of evaluating whether subject impressions aligned with quantitative measures of socket pressure and limb health.

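### The momentary Socket Comfort Score is scheduled apart from socket pressure, so the planned comfort-pressure comparison is weakened and unevenly paired; the label and range of PEQ-13 also need correcting

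*Combined protocol and SAP*

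**What the plan says.** Section 13.0 gives the surveys an interpretive role for both aims: the "survey responses will provide a means of evaluating whether subject impressions aligned with quantitative measures of socket pressure and limb health". It states no statistic for alignment and no rule for pairing a survey with a pressure session.

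Section 7.0 words the Socket Comfort Score as a momentary 0-10 rating: "how would you score the comfort of the socket fit of your artificial limb at the moment". Sections 5.0 and 8.0 place all three surveys at Visits 1, 3 and 5, together with TEWL and laser speckle imaging. Pressure sensors and ambulation trials are at Visits 2, 4 and 6. On the gap, Section 5.0 says, for example, "Study Visit 4 will occur within a week after Visit 3 with a window of 0-7 days"; the same window is given from Visit 1 to 2 and from Visit 5 to 6. Participants may instead choose four visits, which merges Visits 3 and 4 and merges Visits 5 and 6. Visits 1 and 2 stay separate.

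Section 3.2 lists "PEQ, CLASS and Comfort Score responses at 4 weeks" under an outcome about residual limb health. Section 7.0 says that PEQ-13 "focuses on the perceived potential for mobility, ambulation, and transfers while using a prosthetic device", and, on scoring, "The PEQ-13 uses a 100-point formatted visual analog scale with a scoring range of 0 to 130".

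**The concern.** A rating of comfort at one instant is most informative about pressure when both are taken in the same session. The plan treats pressure as session-specific: it is normalised to body weight from that session, and the limb is scanned at the pressure visits to help explain changes in pressure. The comfort score is not collected in those sessions. Day-to-day change in comfort can therefore dilute any relation with pressure. The degree of dilution may also differ between prostheses, and between participants according to a schedule they choose themselves.

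Two smaller matters concern PEQ-13. It measures perceived mobility, which need not move with skin or socket loading: Section 1.0 reports mobility gains with active feet and also raises possible harm to the residual limb. Its stated score range also does not follow from its stated item scale.

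**Working it through.** **Visit pairing.** Inputs: survey visits {1, 3, 5} and pressure visits {2, 4, 6}, from Sections 5.0 and 8.0. The outcomes in Section 3 are at 4 weeks and Section 13.0 compares three prostheses, so three conditions matter.

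| Condition | Comfort score | Pressure | Same visit, six-visit option | Same visit, four-visit option |
|---|---|---|---|---|
| Passive foot | Visit 1 | Visit 2 | No | No |
| Foot A at 4 weeks | Visit 3 | Visit 4 | No | Yes (3 and 4 merged) |
| Foot B at 4 weeks | Visit 5 | Visit 6 | No | Yes (5 and 6 merged) |
| Total | | | 0 of 3 | 2 of 3 |

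By the visit text the gap is 0-7 days, so a same-day pair is possible in the six-visit option but is not scheduled. The calendar windows alone are looser. With Visit 3 at Week 6 and Visit 4 at Week 7, each +/- 7 days, the longest gap is (49 + 7) - (42 - 7) = 21 days. The visit text is the tighter rule and is used here. The expected share choosing four visits is not stated, so it could be anywhere from 0% to 100%.

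**Possible attenuation.** The documents give no between-day correlation for the comfort score; 0.6 to 0.8 is assumed for illustration, with a true same-session comfort-pressure correlation of 0.5. Treat comfort on a given day as a stable part plus a day-specific part.

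- If pressure relates to both parts in proportion, the lagged correlation is the true correlation times the between-day correlation: 0.5 x 0.6 = 0.30, and 0.5 x 0.8 = 0.40.
- If pressure relates only to the stable part, the covariance is the same on either day and the correlation stays at 0.50.

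The illustrative range is therefore about 0.30 to 0.50, which includes no loss. It is not a strict bound: if pressure followed mainly the day-specific part, the result would be lower.

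**PEQ-13 range.** The plan's figure is 0-130, for 13 items on a 100-point scale.

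- Sum: 13 x 100 = 1300, so 0-1300.
- Mean: 1300 / 13 = 100, so 0-100.
- Items scored 0-10: 13 x 10 = 130, so 0-130.

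The stated range is not reproduced from 100-point items. It is reproduced only if each item is scored 0-10 (130 / 13 = 10), which the text does not say.

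**The case against.** The strongest reply is that the surveys are an aid to interpretation, not a tested endpoint, and that the plan already holds usable information. That largely stands:

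- CLASS rates socket fit, including comfort, and its description is not tied to the moment.
- The participant is on the same foot at the survey visit and at the start of the pressure visit that follows.
- The surveys are taken at the same visits as TEWL and perfusion, so the limb-health half of the sentence has no timing problem in either option.

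A reader might therefore infer too much in four places:

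- **That the surveys cannot show alignment with pressure.** The points above rule this out; the comparison is weakened only.
- **That none of seven recorded foot conditions has a comfort score.** The pressure sessions do cover seven (passive; each research foot newly fitted, battery on at 4 weeks and battery off at 4 weeks). But the newly fitted and battery-off trials are not named in any survey comparison, so three is the relevant denominator.
- **That a PEQ-13 gain would be reported as a limb-health result.** Section 13.0 names TEWL and perfusion as the limb-health measures and treats surveys separately as impressions. The listing in Section 3.2 is loose labelling.
- **That a form capped at 130 would truncate scores.** The documents show no form and no cap, and scoring items 0-10 is a plausible reading.

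It can also be said that comfort rated with sensors in the socket, after repeated trials, may be affected by the sensors, fatigue or earlier answers. That is a real downside. It is a reason to keep the existing scores, not a reason to leave the pressure sessions without any.

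**Conclusion.** The point holds in a limited form. In the six-visit option no main condition has the momentary comfort score and pressure at the same visit. In the four-visit option both research feet do and the passive foot does not. Pairing therefore differs by prosthesis and by a schedule the participant chooses. The effect on the comfort-pressure comparison is a weakening of unknown size; the 0.30 to 0.50 range rests entirely on assumed values. The primary outcome, the TEWL and perfusion analyses and the comparisons among prostheses are not affected. The change is worth making because it is cheap and because comfort in a session that was not scored cannot be recovered later. The PEQ-13 label and range are minor corrections.

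**What to change.** 1. At Visits 2, 4 and 6, ask the one-question Socket Comfort Score immediately after the trials with the passive foot and with each research foot at 4 weeks. For the research feet, ask it after the battery-on trials and before the battery-off repeat. Scoring the newly fitted and battery-off conditions is optional.
2. State in Section 13.0 that these values are used for the comfort-pressure comparison. Keep the Visit 1, 3 and 5 scores for comparison with TEWL and perfusion and as a record of comfort without sensors.
3. In Sections 3.2 and 13.0, report PEQ-13 as a functional (mobility) outcome, not under residual limb health.
4. In Section 7.0, reconcile the PEQ-13 range with its items: 0-100 as a mean, 0-1300 as a sum, or state that items are scored 0-10 if 0-130 is intended.

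Cost: one verbal question per condition, taking seconds; an added entry in the study calendar; and short edits to Sections 3.2, 7.0 and 13.0. The downside is that comfort rated with sensors in place may differ from daily comfort, by an amount the documents do not give.

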14.0 Statistical Data Management

14.1 CLINICAL DATA: Will be recorded in RedCap (research electronic data capture (HIPAA compliant) as clinical research database. Prior to being given access to the data, HIPAA and human subjects certified “study staff” will be trained in the collection of patient-reported outcomes. Study data will be collected using standardized case report forms (CRFs), with clear, uniform instructions for study staff. Researcher’s access to files will be governed by institutional secure data access policies. The RedCap platform is developed and operated by IU clinical research IT team.

14.2 DATA QUALITY AND SECURITY. The study team will review all CRFs. All incoming data will be monitored, with particular attention to: 1) enrollment and follow-up reports as entered into the database; 2) potential adverse events, and 3) missing data or extreme values. The clinical database administrator will generate reports of enrollment progress and data quality control results, to be distributed to the study team bi-monthly and ad hoc as needed, as well as to the safety committee.

15.0 Privacy/Confidentiality Issues

15.1 PRIVACY/CONFIDENTIALITY ISSUES. Records of the participation in this study will be held confidential so far as permitted by law. Any information about participants will be obtained from this study will be kept confidential. The sponsor's delegates, IRB, and the United States Food and Drug Administration (FDA) have access to and may copy the medical records applicable for this study therefore absolute confidentiality cannot be guaranteed.

15.2 CLINICAL TRIALS.GOV. A description of this clinical trial will be available on <http://www.clinicaltrials.gov>, as required by U.S. law. This web site will not include information that can identify the participants. At most, the web site will include a summary of the results. The research study coordinator will have access to subject identity. All samples that will undergo analysis will only be identified by a subject code which can only be linked with protected health information (PHI) database by persons who have access to the study database (i.e., research nurses, investigators) via a password. This procedure satisfies HIPAA and is standard for clinical studies run at IU, and as overseen by the IU-CTSA.

16.0 Follow-up and Record Retention

Study results, data, and documentation will be stored for a minimum of 6 years.
